## b. Incident cases and exposure-days

- 1. A seed room was defined as a room containing a patient with microbiologically proven current or history of infection or colonization with one or more target MDROs (i.e., potentially "seeded" by the inhabitant).
- 2. Exposed patient The next patient admitted to the seed room was an "exposed patient."
- 3. Incident case Exposed patients qualified as a potential "incident case" of acquisition if they met the following criteria:
  - In seed room for ≥24 hours AND
  - A positive clinical culture with one of the target MDROs AND
  - The organism identified in the clinical culture was the same target MDRO isolated from the preceding patient in the seed room AND
  - The positive culture was obtained during the index admission either during or after exposure to the seed room *OR*
  - The positive culture was obtained during hospital readmission
    - Within 90 days of discharge for MRSA, VRE, and MDR Acinetobacter
       OR
    - Within 28 days of discharge for C. difficile
- 4. Exposure days Exposure days were calculated as the number of days the exposed patient spent in the seed room. Patients excluded from the numerator were also excluded from the denominator.

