## c. Clinical incidence – Exposed Patients

1. Clinical incidence of MRSA, VRE, C. difficile, or MDRAB among exposed patients

The clinical incidence of all 4 target organisms (rate/10,000 exposure days) will be calculated for each study phase individually.

- a. Numerator: qualifying incident cases of any of the target organisms
- b. Denominator: exposure days for all exposures
- 2. Clinical incidence of *C. difficile* among exposed patients

The clinical incidence of *C. difficile* (rate/10,000 exposure days) will be calculated for each study phase individually.

- a. Numerator: qualifying incident cases of *C. difficile*
- b. Denominator: exposure days among patients exposed to *C. difficile* seed rooms

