#### 8. EFFICACY ANALYSES

# a. Analyses of clinical incidence - primary and secondary outcomes

Incidence rates will be compared between different disinfection protocols (study phases) using Poisson regression model with log of hospital-level number of "first positivity" cases as the outcome, log of hospital-level total days of exposure as an offset term and variables for intervention phase (B: quaternary ammonium + UV light, C: bleach, or D: bleach + UV light; A: standard disinfection will be used as reference), study period in the crossover sequence (1, 2, 3 or 4), and hospital as covariates. Interaction between intervention and study period will be evaluated. Generalized estimating equations (GEE) approach will be used to adjust for clustering by hospital. Individual models will be created for each primary and secondary efficacy outcome.

Each of the three enhanced terminal room disinfection strategies will be compared to the standard strategy; the null hypothesis in each case is that there is no difference in the clinical incidence rate between the enhanced strategy and the standard strategy. Each of the study phases will be compared to study phase A (reference) except for the patient-level analysis of *C. difficile*. As this comparison involved the comparison of bleach vs. bleach + UV-C for exposed patients, results from study phases B and D were compared to results from study phases A and C. Additional analyses will compare interventions using UV light vs those without UV light. In these analyses, variables for UV light (yes/no) and bleach (vs. quaternary ammonium) will replace the variable for intervention in the regression models.

The intention-to-treat (ITT) population will include all exposed patient stays, as described above. Per protocol (PP) population will exclude patient stays during study periods using UV light (phases B and D) if UV light was not documented as used before patient entered the room, or where the room was not in fact a seed room. For the purpose of the PP analysis, the UV device will only have to be turned on in the room; cycle completion will not be required for inclusion. Analyses of the outcomes for exposed patients will be conducted according to ITT and PP populations; analyses of the outcomes for the entire hospital will be conducted on ITT population only. Statistical tests will be performed at a two-sided significance level of 0.05 with no adjustment for multiple comparisons.

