# 10. SAMPLE SIZE AND POWER CONSIDERATIONS

We performed two power calculations prior to the initiation of the study, one for the hospital-level analysis of eligible exposed patients and one for the hospital-wide analysis of all patients admitted to the hospital. Best estimates were made based on review of 4-years of surveillance data from study hospitals and published literature. Prior to our study, the proportion of new colonization/infection that occurs in rooms from which a patient with MRSA, VRE, *C. difficile*, and/or MDR-Acinetobacter was discharged is unknown. All power calculations were performed with two-sided 0.05 significance level.

- a. Eligible exposed patients Our power calculation for this analysis was based on the following assumptions. First, we projected that a total of 7,000 patients would be exposed to a seed room and eligible for inclusion in our study at the 9 study hospitals. Second, all seed rooms would be contaminated. Third, 11% of exposed, eligible patients would develop the outcome of interest. Thus, we projected that the outcome would occur in 190 (11%) of 1,750 patients during the baseline period. Based on these assumptions, our study had 80% power to detect an absolute decrease in the proportion of outcomes caused by the four target organisms of 3% for any of the enhanced disinfection strategies and >99% power to detect an absolute decrease of 5% or more.
- b. **Hospital-wide** Our power calculation for this analysis was based on the following assumptions. First, we projected that 1.96 million patient days of care would be provided at the 9 study hospitals during the study period. Second, for each 6-month intervention period, we projected that approximately 491,200 patient-days of care will occur (distributed across 9 participating hospitals). Third, we projected that 959 outcomes due to the four target organisms would occur during the baseline (or reference) 6-month period, for a baseline incidence rate of 1.95/1,000 patient-days. Under these assumptions, the study had 60% power to detect a 10% decrease in incidence rate, 92% power to detect a 15% decrease and >99% power to detect a 20% decrease.

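### Exposed-patient rates: exposure days do not stop at the first positive culture, and no per-stay analysis tests whether the result depends on counting in-room days

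*SAP*

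**What the plan says.** The point concerns the exposed-patient outcomes only. Hospital-wide rates use patient-days (Section 6d) and are not affected.

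- **Cases.** Section 6b, item 3, accepts a culture from the index admission: "The positive culture was obtained during the index admission either during or after exposure to the seed room". It also accepts a culture at readmission: "Within 90 days of discharge for MRSA, VRE, and MDR Acinetobacter" or "Within 28 days of discharge for C. difficile".
- **Days.** Section 6b, item 4, states: "Exposure days were calculated as the number of days the exposed patient spent in the seed room". The only link to the numerator is "Patients excluded from the numerator were also excluded from the denominator". That rule removes whole patients; it does not cut off days.
- **Event.** Section 3 defines the outcome as a first positive culture, so a patient who has become a case cannot become one again.
- **Use.** Section 6c divides the composite by these days ("Denominator: exposure days for all exposures") and C. difficile by the days in C. difficile seed rooms. Section 8a puts them in the model: "log of hospital-level total days of exposure as an offset term".
- **Power.** Section 10a works with a proportion of patients: "the outcome would occur in 190 (11%) of 1,750 patients".

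Room stay is not a term in the Section 8a model, is not among the potential confounders of Section 6f, and is not listed for reporting by strategy. The one sensitivity analysis (Section 13, post hoc) drops the 24-hour rule and does not change the denominator.

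**The concern.** There are two separate issues.

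First, in-room days after the first positive culture are counted as time at risk. A strategy with more cases collects more such days, which lowers its rate and narrows the contrast with the other strategies.

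Second, the offset makes expected cases proportional to in-room days. Part of the numerator is detected after the patient has left the room, in the rest of the admission or at readmission. If the risk of being counted as a case does not rise fully in proportion to days in the room, a strategy under which exposed patients happen to stay longer will show a lower rate with no change in risk per patient. Room stay is measured after assignment, and nothing planned would let a reader see whether this had happened.

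**Working it through.** **Inputs from the SAP (Section 10a).** 7,000 exposed patients over four strategies: 7,000 / 4 = 1,750 each. Baseline risk 11%: 0.11 × 1,750 = 192.5. The SAP's 190 is 190 / 1,750 = 10.9%, which agrees after rounding. A 3-point decrease gives 8%: 0.08 × 1,750 = 140 cases, and a risk ratio of 0.08 / 0.11 = 0.727.

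**The SAP's own power figure.** For 11% against 8% with 1,750 per strategy, two-sided 0.05, a two-proportion test gives (0.03 − 1.96 × 0.00991) / 0.00990 = 1.07, hence 85.7% power against the stated 80%. The stated figure is conservative. It does not involve exposure days and has no bearing on this point.

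**Assumed inputs.** The SAP gives no room stay, no timing of cultures within the stay, and no share of cases detected in the room. All values for these below are assumptions, shown as ranges.

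**1. Days after the first positive.** Take 5 at-risk days per stay and a true rate ratio of 0.73, so risks of 0.11 and 0.0803. Counted days per stay are d = 5 + risk × share of cases detected in the room × further days. The reported ratio is 0.73 × d(standard) / d(enhanced).

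- Share 0.3, 3 further days: 0.73 × 5.099 / 5.072 = 0.734.
- Share 0.5, 8 further days: 0.73 × 5.440 / 5.321 = 0.746.

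A second layout lets cases stay 1 to 2 times as long as non-cases, with half or all of them detected in the room and 25% to 75% of those cases' days falling after the positive. Its most extreme setting (2 times, all detected in the room, 75%) gives:

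- Days not stopped: 0.727 × 1.11 / 1.08 = 0.747.
- Days stopped: 0.727 × 0.945 / 0.960 = 0.716.

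The difference is about 0.03. For comparison, the standard error of the log rate ratio is √(1/192.5 + 1/140) = 0.11. The shift from 0.73 to 0.746 is ln(0.746 / 0.73) = 0.022, or about 0.2 standard errors.

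**2. Differences in room stay.** Let s be mean room stay under the enhanced strategy divided by that under the standard one, and q the share of risk that does not depend on stay. With no true strategy effect, the ratio per stay is (1 − q)s + q, and the ratio per day is that value divided by s.

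| s | Per day, q = 1 | Per stay, q = 1 | Per day, q = 0.5 | Per stay, q = 0.5 | Per day, q = 0 | Per stay, q = 0 |
|---|---|---|---|---|---|---|
| 0.90 | 1.11 | 1.00 | 1.056 | 0.95 | 1.00 | 0.90 |
| 1.05 | 0.95 | 1.00 | 0.976 | 1.025 | 1.00 | 1.05 |
| 1.10 | 0.91 | 1.00 | 0.955 | 1.05 | 1.00 | 1.10 |
| 1.20 | 0.83 | 1.00 | 0.917 | 1.10 | 1.00 | 1.20 |

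In the extreme case q = 1, with 192.5 events per strategy and pure Poisson variation, the standard error is √(2 / 192.5) = 0.102. The chance of p < 0.05 is then about 8% at s = 1.05, 15% at s = 1.10 and 18% at s = 0.90, against a nominal 5%. With the planned risk ratio of 0.727 and q = 1, the day-based ratio is 0.727 / 1.1 = 0.66 or 0.727 / 0.9 = 0.81.

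Neither denominator is neutral throughout: per-day is exact at q = 0, per-stay is exact at q = 1, and between them both are off, in opposite directions.

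**The case against.** The SAP calls the denominator exposure days, that is, time in contact with a possibly contaminated room. The later windows can be read as detection periods for acquisition during that contact. Cases per unit of exposure is a legitimate estimand, and the 24-hour rule shows that the team thought of room time as exposure. The room is disinfected before the exposed patient enters, every hospital uses all four strategies, and the model has hospital and period terms, so there is no obvious reason for stay to differ by strategy. Days after the event have a negligible effect, and it runs toward 1. That these days are counted is inferred from a definition that names no stopping point; the SAP does not say so outright.

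Most of this stands. It rules out three stronger conclusions that a reader might draw:

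- **That any stay difference passes one-for-one into the rate ratio.** This needs q = 1, which the SAP neither states nor implies.
- **That the post-event days are why the ratio responds to room stay.** They are not; the response comes from using a day-based offset at all.
- **That the proportion used for power shows the day-based model to be wrong.** Sizing on a proportion and analysing a rate does not bias the rate ratio.

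What the objection does not answer is that proportionality is assumed without a stated rationale, that part of the numerator arises after the patient leaves the room, and that nine hospitals with a crossover limit but do not exclude chance differences in stay.

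**Conclusion.** As written, Section 6b counts days after the first positive as time at risk. That is a small flaw: the rate ratio moves toward 1 by 0.004 to 0.016 in the first layout and by at most about 0.03 in the second, all under assumed stays.

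The reliance on in-room days is a robustness gap. Its possible size at a 10% longer stay runs from none (risk fully proportional to stay) through 0.955 (half independent of stay) to 0.91 (fully independent). A reader might infer that the primary rate ratios are biased by room stay. The SAP does not support that: it gives no room stay by strategy, and the differences used above are assumptions. Nor does it support replacing the day denominator, which would change the estimand and distort in the other direction when risk does rise with room time. The point is a cheap improvement and no threat to the design.

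**What to change.** 1. In Section 6b, item 4, end exposure days at the earlier of leaving the seed room and the first positive culture that makes the patient a case.
2. Keep the day-based model of Section 8a as the lead analysis, and give in one sentence the reason for using in-room days.
3. Add one sensitivity model per primary outcome, identical except that the offset is the log of the number of exposed stays: all exposed stays for the composite, and stays in C. difficile seed rooms for the second endpoint. Pre-specify it if outcome data have not been examined; otherwise label it post hoc, as Section 13 already does for the 24-hour rule.
4. Report mean and median room stay by strategy.
5. State that, if the two scales disagree, the result will be reported as depending on the denominator, without presuming that either is right.

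The cost is one line in the derivation, a small table, and one supportive estimate per primary outcome. Because no multiplicity adjustment is planned, the text should say that this estimate is not used for the primary conclusion. The counts should be available from the bed-flow and microbiology data already combined for the endpoint.

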## c. Clinical incidence – Exposed Patients

1. Clinical incidence of MRSA, VRE, C. difficile, or MDRAB among exposed patients

The clinical incidence of all 4 target organisms (rate/10,000 exposure days) will be calculated for each study phase individually.

- a. Numerator: qualifying incident cases of any of the target organisms
- b. Denominator: exposure days for all exposures
- 2. Clinical incidence of *C. difficile* among exposed patients

The clinical incidence of *C. difficile* (rate/10,000 exposure days) will be calculated for each study phase individually.

- a. Numerator: qualifying incident cases of *C. difficile*
- b. Denominator: exposure days among patients exposed to *C. difficile* seed rooms

## 3. Clinical incidence of MRSA among exposed patients

The clinical incidence of MRSA (rate/10,000 exposure days) will be calculated for each study phase individually.

- a. Numerator: qualifying incident cases of MRSA
- b. Denominator: exposure days among patients exposed to MRSA seed rooms

## 4. Clinical incidence of VRE among exposed patients

The clinical incidence of VRE (rate/10,000 exposure days) will be calculated for each study phase individually.

- a. Numerator: qualifying incident cases of VRE
- b. Denominator: exposure days among patients exposed to VRE seed rooms

## 5. Clinical incidence of MDRAB among exposed patients

The clinical incidence of MDRAB (rate/10,000 exposure days) will be calculated for each study phase individually.

- c. Numerator: qualifying incident cases of MDRAB
- d. Denominator: exposure days among patients exposed to MDRAB seed rooms

## d. Clinical incidence – All Patients Admitted to the Hospital

Hospital-wide clinical incidence was calculated as the number of patients with hospital-acquired incidence of a target MDRO/10,000 patient days among patients who stayed in the hospital for at least 48 hours. Patients did not have to be "exposed" to a seed room to qualify for these analyses, though the same exclusion criteria were otherwise applied.

## 1. Hospital-wide clinical incidence of MRSA, VRE, C. difficile, or MDRAB

The clinical incidence of all 4 target organisms (rate/10,000 patient days) will be calculated for each study phase individually.

- a. Numerator: qualifying incident cases of any of the target organisms
- b. Denominator: patient days

## 2. Hospital-wide clinical incidence of *C. difficile*

The clinical incidence of *C. difficile* (rate/10,000 patient days) will be calculated for each study phase individually.

- a. Numerator: qualifying incident cases of C. difficile
- b. Denominator: patient days

## 3. Hospital-wide clinical incidence of MRSA

The clinical incidence of MRSA (rate/10,000 patient days) will be calculated for each study phase individually.

- a. Numerator: qualifying incident cases of MRSA
- b. Denominator: patient days

## 4. Hospital-wide clinical incidence of VRE

The clinical incidence of VRE (rate/10,000 patient days) will be calculated for each study phase individually.

- a. Numerator: qualifying incident cases of VRE
- b. Denominator: patient days

## 5. Hospital-wide clinical incidence of MDRAB

The clinical incidence of MDRAB (rate/10,000 patient days) will be calculated for each study phase individually.

- a. Numerator: qualifying incident cases of MDRAB
- b. Denominator: patient days

## e. Measures for monitoring protocol fidelity

## 1. Use of the UV device on eligible contact precaution rooms

Compliance with use of the UV device will be calculated as a proportion:

- a. Numerator: uses of the machine
- b. Denominator: rooms of patients on contact precautions, as derived from infection prevention databases

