## 3. Adverse outcomes

- a. Missed opportunities rate and description. We will summarize the number of times a UV-C device failed to be used and, if available, the reason it wasn't used.
- b. Time on diversion days per 6-month study period, as determined using bed control administrative logs from study hospitals.
- c. Emergency room wait time minutes per patient, as determined using bed flow data from study hospitals.
- d. Questionnaire results HCW perception of cleaning methods
- e. Room cleaning time minutes per room, as determined using bed flow and environmental services work flow datasets from study hospitals.

The term "first positivity" is defined as the first time (either colonization or infection) a clinical culture grows MRSA, VRE, *C difficile*, or MDRAB in an exposed patient. The terms "first positivity" and "clinical incidence" are used interchangeably (Ellingson, Jernigan ICHE 2011; Cohen ICHE 2008). Clinical incidence is the most appropriate term, as our data relied on routine clinical activities. While we use the term "patient-level" analyses, all analyses are actually at the hospital level. We changed the number of patients' data included in analyses by either including only those who met our criteria as exposed (i.e., primary outcomes and secondary outcomes b.1.) or all patients in the hospital (i.e., secondary outcomes b.2.). In both instances, patients could have had multiple admissions and, potentially, multiple exposures.

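### UV compliance in SAP Section 6e.1 divides device uses by rooms without linking the two, so it can exceed 1 and misstate fidelity in either direction

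*SAP*

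**What the plan says.** Section 6e lists the fidelity measures. Item 1 is headed "Use of the UV device on eligible contact precaution rooms" and states: "Compliance with use of the UV device will be calculated as a proportion". Its two components are "Numerator: uses of the machine" and "Denominator: rooms of patients on contact precautions, as derived from infection prevention databases".

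Three other places bear on it:

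- **Section 4b** says that in practice the strategies are applied to contact-precaution rooms. For analysis, a room becomes eligible when a patient with a listed organism leaves it by transfer or discharge after more than 24 hours there.
- **Section 3b, item 3a** names a missed-opportunities rate and describes it thus: "We will summarize the number of times a UV-C device failed to be used and, if available, the reason it wasn't used". No denominator is given.
- **Section 8a** excludes stays in phases B and D from the per-protocol population "if UV light was not documented as used before patient entered the room, or where the room was not in fact a seed room". For that analysis, "the UV device will only have to be turned on in the room; cycle completion will not be required for inclusion". The hospital-wide outcomes have no per-protocol analysis.

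**The concern.** In a proportion, the numerator is a subset of the denominator. Here one side counts uses and the other counts rooms, and no rule connects them. Two uses in one room can cancel one untreated room. A contact-precaution room whose patient has not left can sit in the denominator although no terminal cleaning is yet due.

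The neighbouring measures are built correctly. Hand hygiene compliance (Section 6f.1) divides correct events by observed events, and room cleaning compliance (Section 6f.2) divides markers removed by markers applied.

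What is at stake is interpretation. If a UV strategy shows no benefit, readers will ask whether UV was delivered. For exposed patients the per-protocol analysis helps to answer that. For the hospital-wide outcomes it does not exist, and the Section 6e.1 ratio is the only UV-delivery rate for which the SAP states a formula.

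**Working it through.** The SAP states no compliance value, so there is no figure to reproduce. The check has two parts.

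**1. The text, side by side**

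| Element | Section 6e.1 | What a proportion of rooms treated needs |
|---|---|---|
| Numerator unit | Device uses | Cleanings treated at least once |
| Denominator unit | Contact-precaution rooms | Cleanings when UV was due (discharge or transfer, Section 4b) |
| Link between them | None stated | Each numerator item belongs to the denominator |
| Repeat uses | No rule | Counted once |

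**2. How far the ratio can move**

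Write the reported ratio as

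R = [c(1 + r) + o] / k

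- c: true share of eligible terminal cleanings treated at least once
- r: extra uses per treated cleaning
- o: uses in other rooms, per eligible cleaning
- k: listed contact-precaution rooms divided by terminal cleanings at which UV was due

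None of these is in the documents. The assumed ranges are c from 0.70 to 0.90, r from 0 to 0.20, and k from 1 to 1.25. I set o = 0 because the heading confines the measure to eligible contact-precaution rooms.

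| c | r | k | Calculation | R |
|---|---|---|---|---|
| 0.80 | 0.10 | 1 | 0.80 × 1.10 | 0.88 |
| 0.80 | 0.20 | 1 | 0.80 × 1.20 | 0.96 |
| 0.90 | 0.20 | 1 | 0.90 × 1.20 | 1.08 |
| 0.80 | 0 | 1.10 | 0.80 / 1.10 | 0.73 |
| 0.80 | 0 | 1.25 | 0.80 / 1.25 | 0.64 |
| 0.80 | 0.10 | 1.10 | 0.88 / 1.10 | 0.80 |

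The third row is impossible for a proportion. The first two overstate a true 0.80, the fourth and fifth understate it, and in the last the two errors cancel. The numerator error alone can only inflate or do nothing. An over-broad denominator deflates, so the net sign is open.

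With numerator and denominator both counted as eligible terminal cleanings, R = c and cannot exceed 1.

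**The case against.** The strongest reply is that this is loose drafting in a monitoring measure, and that other parts of the SAP carry the weight. Much of that stands.

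- *Uses anywhere count as compliance.* A reader might infer this from the bare numerator line. The heading restricts the measure to eligible contact-precaution rooms, so the text supports only an ambiguity. If other-room uses were counted at an assumed o = 0.05, the first row above would become 0.88 + 0.05 = 0.93, but the point does not need that term.
- *Restarted cycles are counted twice.* The SAP does not define a use for Section 6e.1 and never mentions restarts. The turned-on rule is given for the per-protocol analysis only, where a stay is simply in or out. Double counting is something the formula permits. The SAP does not prescribe it.
- *Fidelity is overstated and missed rooms are hidden.* The documents do not support this. The direction is unknown, as shown above, and Section 3b plans a separate report of missed uses.
- *This is the only evidence of UV delivery.* It is not. Section 8a uses documentation of UV before the patient entered the room, for exposed stays.
- *It changes the efficacy results.* It does not. The ratio enters no model in Section 8a, defines no population, and is not among the Section 6f and 7 variables that Section 11b allows as covariates.

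The objection does not remove the formula itself. The missed-opportunities item is called a rate but has no denominator. It is not derived in Section 6g and is not among the three outcomes that Section 9 says will be analysed. The per-protocol documentation covers exposed stays only.

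**Conclusion.** The point holds as a defect of definition. Section 6e.1 labels as a proportion a ratio of unlinked quantities in different units, with a denominator not tied to the moment when UV is due. It can exceed 1 and can err in either direction. The size for this trial cannot be determined from the SAP. The range of 0.64 to 0.96 around a true 0.80 rests wholly on assumed repeat-use rates of up to 20% and a denominator up to 25% too large.

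The effect is confined to how UV delivery is reported and to how results are interpreted, most of all the hospital-wide outcomes. It should be corrected, but it does not threaten the primary analysis.

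**What to change.** Reword Section 6e.1 as follows:

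- **Denominator:** terminal cleanings of eligible contact-precaution rooms in phases B and D, with eligibility stated by reference to Section 4b.
- **Numerator:** those cleanings with at least one documented UV use between the source patient's departure and the next patient's entry, each counted once.
- **Missed opportunities (Section 3b, item 3a):** use the same denominator, so that the rate named there can be calculated.

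Section 6a says that all variables are calculated in all four phases. Naming phases B and D also settles where UV compliance applies.

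The cost is SAP wording and some record linkage. The per-protocol rule already needs UV documentation by room and time for exposed stays, and the same link would have to be extended to eligible cleanings outside that set. The reported compliance may come out less favourable.
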